## 2.2 Rationale

The concentration of CB-03-01 selected for the initial clinical studies (1%) was based on antiandrogenic activity in the hamster flank organ test in which the best effective concentration was 0.8% (5). The results of the Phase 2 Dose Escalation Study demonstrated that CB-03-01 cream, 1% applied BID had more favorable results than other treatments (0.1% BID, 0.5% BID, and 1% QD) and no material safety issues were noted with any of the concentrations of CB-03-01 cream (6). Based on the collective findings of the previous Phase 1 and Phase 2 studies, CB-03-01 cream, 1% BID appears to be the best treatment candidate to advance for further clinical study and development as a topical treatment for acne vulgaris. Thus, the present Phase 3 study has been designed to determine and compare the efficacy of treatment with CB-03-01 cream, 1% and the vehicle cream applied twice daily for 12 weeks in subjects with moderate to severe facial acne vulgaris.

## 2.3 Study Objectives

The primary objective of this study is to determine the safety and efficacy of CB-03-01 cream, 1% versus the vehicle cream applied twice daily for 12 weeks in subjects with facial acne vulgaris.

## 2.4 Study Design

This is a multicenter, randomized, double-blind, vehicle-controlled, parallel-group comparison study of safety and efficacy for CB-03-01 cream, 1% in male and female subjects 9 years or older with moderate to severe acne vulgaris on the face. Eligible subjects must have acne vulgaris of the face (which can include the nose) with an Investigator's Global Assessment (IGA) score of 3 or 4, at least 30 to a maximum of 75 inflammatory lesions

(papules, pustules, and nodules) and at least 30 to a maximum of 100 non-inflammatory lesions (open and closed comedones). 732 subjects were enrolled at 48 sites (5 sites included into the study did not enroll any subject). Subjects were randomized in a 1:1 ratio to one of two treatment groups:

1. CB-03-01 cream containing 1% cortexolone 17 $\alpha$ -propionate
2. Vehicle cream

All subjects had to apply the assigned test article to the face twice daily for 12 weeks. Refer to section 6 of the study protocol (4).

## 2.5 Study Population

Male and female subjects 9 years or older with facial acne vulgaris (Grade 3 or 4 on Investigator's Global Assessment [IGA]).

732 subjects were included into the study and 53 sites participated in this study (5 sites did not enroll any subject).

### 2.5.1 Subject Eligibility

To be included in the study, subjects had to meet the inclusion criteria and none of the exclusion criteria reported in the section 5.1.1 and 5.1.2 of the study protocol (4).

### 2.5.2 Subject Withdrawal Criteria

Procedures for handling subjects who were discontinued from the study are described in section 13.2 of the study protocol (4). Subjects who were discontinued were not replaced.

## 2.6 Randomization Assignment

Subjects who were eligible for enrollment into the study were randomized to receive CB-03-01 cream or vehicle cream in a 1:1 ratio. The randomization scheme was blocked by investigational site with a block size of 4. At each site, subject kits were dispensed according to the kit number assigned by an IVRS/IWRS system as subjects were enrolled. At each site, the study staff added the site number (provided to each site) and the subject number (starting with 001) to each kit label. The kit number dispensed to each subject was also recorded on the source documents and CRFs. Treatment group designation will remain blinded until the final database is locked, unless unblinding is required as described in section 15 of the study protocol (4). Subjects who withdrew prematurely from the study were not replaced.

### 3. CLINICAL EVALUATIONS AND LABORATORY TESTS

The following clinical evaluations were performed according to the schedules indicated during the study. The same investigator should have completed the evaluations for a given subject throughout the study. If this became impossible a sub-investigator with overlapping experience with the subject and the study should have completed the evaluations.

#### 3.1 Investigator's Global Assessment (IGA)

At every study visit, overall severity of acne using a five-point scale from 0 (clear) to 4 (severe) was assessed. This is a static morphological scale that refers to a point in time and not a comparison to Baseline. Subjects had to have an IGA score of 3 (moderate) or 4 (severe) at Baseline.

Score	Assessment	Description
0	Clear	Absence of active disease with no inflammatory or non-inflammatory lesions
1	Almost Clear	Rare non-inflammatory lesions with no more than one small inflammatory lesions
2	Mild	Some non-inflammatory lesions with no more than a few inflammatory lesions (papules/pustules only; no nodular/cystic lesions)
3	Moderate	Up to many non-inflammatory lesions and may have some inflammatory lesions but no more than one nodular/cystic lesion
4	Severe	Up to many non-inflammatory lesions and inflammatory lesions but no more than a few nodular/cystic lesions

#### 3.2 Acne Lesions Counting

The number of inflammatory lesions (papules, pustules, and nodules) and non-inflammatory lesions (open and closed comedones) on the face vertically from the hairline to mandible rim and horizontally from ear to ear, including those on the nose were counted to determine subject eligibility at Visit 1. Subjects must have at least 30 to a maximum of 75 inflammatory lesions and 30 to a maximum of 100 non-inflammatory lesions on the face (which can include the nose) at Baseline.

Lesions are defined as follows:

1. Comedones - open (blackheads) and closed (whiteheads).
2. Papules - raised inflammatory lesions with no visible purulent material.
3. Pustules - raised inflammatory lesions with visible purulent material.
4. Nodules - Any circumscribed, inflammatory masses greater or equal to 5 mm in diameter with or without cystic changes.

### 3.3 Fitzpatrick Skin Type Assessment

At Visit 1, the investigator or designee had to document the subject's skin phototype (I-VI) using the Fitzpatrick Skin Type Assessment as described below:

Skin Phototype	Typical Features	Tanning ability
I	Pale white skin, blue/hazel eyes, blond/red hair	Always burns, does not tan
II	Fair skin, blue eyes	Burns easily, tans poorly
III	Darker white skin	Tans after initial burn
IV	Light brown skin	Burns minimally, tans easily
V	Brown skin	Rarely burns, tans darkly easily
VI	Dark brown or black skin	Never burns, always tans darkly

### 3.4 Local Skin Reactions (LSRs)

At every study visit, the investigator or designee had to document the severity of the following LSRs known to be associated with application of topical steroids:

1. Telangiectasia
2. Skin atrophy
3. Striae rubrae

A five-point ordinal scale was used to assess the severity of these reactions:

Score	Assessment
0	None
1	Trace
2	Mild
3	Moderate
4	Severe

In addition, the investigator or designee had to evaluate the severity of the following LSRs known to be associated with acne vulgaris, using the five-point ordinal scales described below:

4. Erythema
5. Edema
6. Scaling/dryness

Erythema Score	Assessment
0	None
1	Minimal - barely perceptible erythema
2	Mild - predominantly minimal erythema (pink) in the treated area with or without a few isolated areas of more intense erythema
3	Moderate - predominantly moderate erythema (red) in the treated area with or without a few isolated areas of intense erythema (bright red)
4	Severe - predominantly intense erythema (bright red) in the treated area with or without a few isolated areas of very intense (fiery red) erythema

Edema Score	Assessment
0	None
1	Minimal - scant, rare edema
2	Mild - easily seen edema, minimally palpable, involving up to 1/3 of the Treatment Area
3	Moderate - easily seen edema and typically palpable, involving between 1/3 to 2/3 of the Treatment Area
4	Severe - easily seen edema, indurated in some areas, involving over 2/3 of the Treatment Area

Scaling/dryness Score	Assessment
0	None
1	Minimal - barely perceptible desquamation
2	Mild - limited areas of fine desquamation in up to 1/3 of the treatment area
3	Moderate - fine desquamation involving 1/3 to 2/3 of the treatment area or limited areas of coarser scaling
4	Severe - coarser scaling involving more than 2/3 of the treatment area or limited areas of very coarse scaling

In addition, subjects were asked to rate the severity of the following LSRS that occurred in the treatment area since the last visit, using the four-point ordinal scales described below:

7. Stinging/burning
8. Pruritus

Stinging/burning Score	Assessment
0	None
1	Minimal, barely perceptible - tolerable and little discomfort
2	Moderate - tolerable, but causes some discomfort
3	Severe - very uncomfortable or intolerable

Pruritus (itching) Score	Assessment
0	None - no evidence of itching
1	Mild - only aware of itching at times, only present when relaxing, not present when focused on other activities
2	Moderate - often aware of itching, annoying, sometimes disturbs sleep and daytime activities
3	Severe - constant itching, distressing; frequent sleep disturbance, interferes with activities

These LSRs were collected independently of AEs. Only LSRs that require medical intervention (e.g., prescription medication) or require withholding the application of the test articles had to be documented as AEs. Any LSRs that are not listed above had to be recorded as AEs.

### 3.5 Urine Pregnancy Tests (UPTs)

The UPT had to be performed at the study site if the site is registered and conforms to Clinical Laboratory Improvement Amendments (CLIA) regulations for such testing (site possesses at a minimum a current valid CLIA Certificate of Waiver) or at an appropriately registered reference laboratory. A UPT had to be performed on all WOCBP at Visit 1 (Baseline), Visit 2, Visit 3 and Visit 4 (or end of treatment if the subject withdraws prematurely). The investigator had to report the UPT results on the CRFs, in the subject's medical records and, if applicable, in independent records maintained at the study site. The UPT used must have a minimum sensitivity of 25mIU of  $\beta$ -HCG/mL of urine.

## 4. STATISTICAL CONSIDERATIONS

### 4.1 Study Endpoints

#### 4.1.1 Efficacy Endpoints

##### 4.1.1.1 Primary Efficacy Endpoints

- P1:** Proportion of subjects in each treatment group with at least a two-point reduction in IGA compared to Baseline AND an IGA score of 0 (clear) or 1 (almost clear) at Week 12 ( $\pi_{2p(0,1)}$ );
- P2:** Absolute change from Baseline in non-inflammatory lesions count (NILC) in each treatment group at Week 12;
- P3:** Absolute change from Baseline in inflammatory lesions count (ILC) in each treatment group at Week 12.

##### 4.1.1.2 Secondary Efficacy Endpoints

- S1:** Absolute change from Baseline in total lesions count (TLC, including inflammatory and non-inflammatory lesions) in each treatment group at Week 12;
- S2:** Percent change from Baseline in total lesions count (TLC, including inflammatory and non-inflammatory lesions) in each treatment group at Week 12;
- S3:** Percent change from Baseline in non-inflammatory lesions count (NILC) in each treatment group at Week 12;
- S4:** Percent change from Baseline in inflammatory lesions count (ILC) in each treatment group at Week 12.

#### 4.1.2 Safety Endpoints

- SF1:** Local and systemic AEs at every visit (Baseline, Weeks 4, 8, and 12);
- SF2:** Local Skin Reactions (telangiectasia, skin atrophy, striae rubrae, erythema, edema, scaling/dryness, stinging/burning and pruritus) scored by frequency and severity at every visit (Baseline, Weeks 4, 8 and 12);
- SF3:** UPTs in all WOCBP at Visit 1 (Baseline), Visit 2, Visit 3 and Visit 4 (or end of treatment if the subject withdraws prematurely);
- SF4:** Material changes from Baseline in ECGs at Week 12.

### 4.2 Hypothesis Tests

Hypothesis tests on the primary endpoints will be conducted according to the following hierarchical order:

- HT1:** Superiority of TEST vs. VEHICLE in terms of the proportion of subjects in each treatment group with at least a two-point reduction in IGA compared to Baseline AND an IGA score of 0 (clear) or 1 (almost clear) at Week 12 ( $\pi_{2p(0,1)}$ );
- HT2:** Superiority of TEST vs. VEHICLE in terms of absolute change from Baseline in non-inflammatory lesions count (NILC) at Week 12;
- HT3:** Superiority of TEST vs. VEHICLE in terms of absolute change from Baseline in inflammatory lesions count (ILC) at Week 12.

The null hypotheses of the three hypothesis tests on the primary endpoints have all to be rejected in order to claim superiority of TEST vs. VEHICLE.

In order to keep an overall Type I error  $\alpha=0.05$  two-sided for the whole study, all the hypothesis tests have to be performed at the same significance level  $\alpha=0.05$  two-sided and the failure to reject a null hypothesis will imply the failure of rejecting of all the subsequent null hypotheses.

This approach inflates the overall Type II error  $\beta$ , which in the worst case scenario is equal to the sum of the Type II error  $\beta$  connected with the individual hypothesis tests. This inflation must be taken into account for a proper estimation of the sample size (3).

Hypothesis tests on the secondary endpoints will be conducted according to the following hierarchical order:

**HT4:** Superiority of TEST vs. VEHICLE in terms of absolute change from Baseline in total lesions count (TLC) at Week 12;

**HT5:** Superiority of TEST vs. VEHICLE in terms of percent change from Baseline in total lesions count (TLC) at Week 12;

**HT6:** Superiority of TEST vs. VEHICLE in terms of percent change from Baseline in non-inflammatory lesions count (NILC) at Week 12;

**HT7:** Superiority of TEST vs. VEHICLE in terms of percent change from Baseline in inflammatory lesions count (ILC) at Week 12.

The hypothesis test for the secondary endpoints will be performed at the same significance level  $\alpha=0.05$  two-sided of the primary endpoints if and only if all the null hypotheses on the primary endpoints are rejected and the failure to reject a null hypothesis will imply the failure of rejecting of all the subsequent null hypotheses.

#### 4.2.1 *Superiority of TEST vs. VEHICLE in terms of the proportion of subjects with at least a two-point reduction in IGA compared to Baseline AND an IGA score of 0 (clear) or 1 (almost clear) at Week 12*

$\pi_{2p(0,1),TEST}$ : Proportion of subjects in TEST treatment group achieving “success” at Week 12, with “success” defined as at least a two-point reduction in IGA compared to Baseline AND an IGA score of 0 (clear) or 1 (almost clear)

$\pi_{2p(0,1),VEHICLE}$ : Proportion of subjects in VEHICLE treatment group achieving “success” at Week 12, with “success” defined as at least a two-point reduction in IGA compared to Baseline AND an IGA score of 0 (clear) or 1 (almost clear)

$$OR_{2p(0,1),TV} = \frac{\pi_{2p(0,1),TEST}(1 - \pi_{2p(0,1),VEHICLE})}{\pi_{2p(0,1),VEHICLE}(1 - \pi_{2p(0,1),TEST})}$$

$$HT1: \begin{cases} H_0: OR_{2p(0,1),TV} \leq 1 \\ H_a: OR_{2p(0,1),TV} > 1 \end{cases}$$

#### 4.2.2 Superiority of TEST vs. VEHICLE in terms of absolute change from Baseline in NILC at Week 12

$\mu_{\text{NILC,TEST}}$ : Mean absolute change from baseline of NILC at Week 12 in TEST treatment group

$\mu_{\text{NILC,VEHICLE}}$ : Mean absolute change from baseline of NILC at Week 12 in VEHICLE treatment group

$$\text{HT2: } \begin{cases} \text{H}_0: \mu_{\text{NILC,TEST}} - \mu_{\text{NILC,VEHICLE}} \leq 0 \\ \text{H}_a: \mu_{\text{NILC,TEST}} - \mu_{\text{NILC,VEHICLE}} > 0 \end{cases}$$

#### 4.2.3 Superiority of TEST vs. VEHICLE in terms of absolute change from Baseline in ILC at Week 12

$\mu_{\text{ILC,TEST}}$ : Mean absolute change from baseline of ILC at Week 12 in TEST treatment group

$\mu_{\text{ILC,VEHICLE}}$ : Mean absolute change from baseline of ILC at Week 12 in VEHICLE treatment group

$$\text{HT3: } \begin{cases} \text{H}_0: \mu_{\text{ILC,TEST}} - \mu_{\text{ILC,VEHICLE}} \leq 0 \\ \text{H}_a: \mu_{\text{ILC,TEST}} - \mu_{\text{ILC,VEHICLE}} > 0 \end{cases}$$

#### 4.2.4 Superiority of TEST vs. VEHICLE in terms of absolute change from Baseline in TLC at Week 12

$\mu_{\text{TLC,TEST}}$ : Mean absolute change from baseline of TLC at Week 12 in TEST treatment group

$\mu_{\text{TLC,VEHICLE}}$ : Mean absolute change from baseline of TLC at Week 12 in VEHICLE treatment group

$$\text{HT4: } \begin{cases} \text{H}_0: \mu_{\text{TLC,TEST}} - \mu_{\text{TLC,VEHICLE}} \leq 0 \\ \text{H}_a: \mu_{\text{TLC,TEST}} - \mu_{\text{TLC,VEHICLE}} > 0 \end{cases}$$

#### 4.2.5 Superiority of TEST vs. VEHICLE in terms of percent change from Baseline in TLC at Week 12

$P_{\text{TLC,TEST}}$ : Mean percent change from baseline of TLC at Week 12 in TEST treatment group

$P_{\text{TLC,VEHICLE}}$ : Mean percent change from baseline of TLC at Week 12 in VEHICLE treatment group

$$\text{HT5: } \begin{cases} \text{H}_0: P_{\text{TLC,TEST}} - P_{\text{TLC,VEHICLE}} \leq 0 \\ \text{H}_a: P_{\text{TLC,TEST}} - P_{\text{TLC,VEHICLE}} > 0 \end{cases}$$

#### 4.2.6 Superiority of TEST vs. VEHICLE in terms of percent change from Baseline in NILC at Week 12

$P_{NILC,TEST}$ : Mean percent change from baseline of NILC at Week 12 in TEST treatment group

$P_{NILC,VEHICLE}$ : Mean percent change from baseline of NILC at Week 12 in VEHICLE treatment group

$$HT6: \begin{cases} H_0: P_{NILC,TEST} - P_{NILC,VEHICLE} \leq 0 \\ H_a: P_{NILC,TEST} - P_{NILC,VEHICLE} > 0 \end{cases}$$

#### 4.2.7 Superiority of TEST vs. VEHICLE in terms of percent change from Baseline in ILC at Week 12

$P_{TLC,TEST}$ : Mean percent change from baseline of ILC at Week 12 in TEST treatment group

$P_{TLC,VEHICLE}$ : Mean percent change from baseline of ILC at Week 12 in VEHICLE treatment group

$$HT7: \begin{cases} H_0: P_{TLC,TEST} - P_{TLC,VEHICLE} \leq 0 \\ H_a: P_{TLC,TEST} - P_{TLC,VEHICLE} > 0 \end{cases}$$

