**4.3.2 Absolute change from baseline in NILC in each treatment group at Week 12**

$$N_{\text{TEST}} = N_{\text{VEHICLE}} = \frac{2\sigma^2(z_{\alpha/2} + z_{\beta})^2}{(\mu_{\text{NILC,TEST}} - \mu_{\text{NILC,VEHICLE}})^2}$$

A post-hoc analysis of the data collected in the Phase 2 Dose Escalation Study 171-7151-201 (6) performed only for the subjects with 30-75 inflammatory lesions and 30-100 non-inflammatory lesions at baseline provided the following results for the least square means (i.e. the means obtained after having controlled for the fixed effects and the covariate of the ANCOVA) of the absolute change from baseline in non-inflammatory lesions count and for the related sample size estimation.

	Number of subjects	Least Square Mean
TEST	24	-22.398746
VEHICLE	22	-0.924803

Considering a mean absolute change from baseline in non-inflammatory lesions count of **-22** for TEST treatment group and **-1** for VEHICLE treatment group and a common standard deviation of **17**, we obtain the following estimate of the sample size.

$$\alpha = 0.05 \text{ two - sided}, \beta = 0.033, \mu_{\text{ILC,TEST}} = -22, \mu_{\text{ILC,VEHICLE}} = -1, \sigma = 17$$

$$N_{\text{TEST}} = N_{\text{VEHICLE}} = 19$$

**19 subjects per group** should be enrolled in order to have 19 subjects per group included into the ITT Set.

#### 4.3.3 Absolute change from Baseline in ILC in each treatment group at Week 12

$$N_{\text{TEST}} = N_{\text{VEHICLE}} = \frac{2\sigma^2(z_{\alpha/2} + z_{\beta})^2}{(\mu_{\text{ILC,TEST}} - \mu_{\text{ILC,VEHICLE}})^2}$$

A post-hoc analysis of the data collected in the Phase 2 Dose Escalation Study 171-7151-201 (6) performed only for the subjects with 30-75 inflammatory lesions and 30-100 non-inflammatory lesions at baseline provided the following results for the least square means (i.e. the means obtained after having controlled for the fixed effects and the covariate of the ANCOVA) of the absolute change from baseline in inflammatory lesions count and for the related sample size estimation.

	Number of subjects	Least Square Mean
TEST	24	-14.473098
VEHICLE	22	-10.621723

Considering a mean absolute change from baseline in inflammatory lesions count of **-15** for TEST treatment group and **-10** for VEHICLE treatment group and a common standard deviation of **17**, we obtain the following estimate of the sample size.

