$$\alpha = 0.05 \text{ two - sided}, \beta = 0.033, \mu_{\text{ILC,TEST}} = -15, \mu_{\text{ILC,VEHICLE}} = -10, \sigma = 17$$

$$N_{\text{TEST}} = N_{\text{VEHICLE}} = 334$$

**334 subjects per group** should be enrolled in order to have 334 subjects per group included into the ITT Set.

#### 4.3.4 Absolute change from Baseline in TLC at Week 12

$$N_{\text{TEST}} = N_{\text{VEHICLE}} = \frac{2\sigma^2(z_{\alpha/2} + z_{\beta})^2}{(\mu_{\text{TLC,TEST}} - \mu_{\text{TLC,VEHICLE}})^2}$$

A post-hoc analysis of the data collected in the Phase 2 Dose Escalation Study 171-7151-201 (6) performed only for the subjects with 30-75 inflammatory lesions and 30-100 non-inflammatory lesions at baseline provided the following results for the least square means (i.e. the means obtained after having controlled for the fixed effects and the covariate of the ANCOVA) of the absolute change from baseline in total lesions count and for the related sample size estimation.

	Number of subjects	Least Square Mean
TEST	24	-35.7127562
VEHICLE	22	-13.0667959

Considering a mean absolute change from baseline in total lesions count of **-35** for TEST treatment group and **-13** for VEHICLE treatment group and a common standard deviation of **17**, we obtain the following estimate of the sample size.

$$\alpha = 0.05 \text{ two - sided}, \beta = 0.1, \mu_{\text{TLC,TEST}} = -35, \mu_{\text{TLC,VEHICLE}} = -13, \sigma = 17$$

$$N_{\text{TEST}} = N_{\text{VEHICLE}} = 13$$

**13 subjects per group** should be enrolled in order to have 13 subjects per group included into the ITT Set.

#### 4.3.5 Percent change from Baseline in TLC at Week 12

$$N_{\text{TEST}} = N_{\text{VEHICLE}} = \frac{2\sigma^2(z_{\alpha/2} + z_{\beta})^2}{(P_{\text{TLC,TEST}} - P_{\text{TLC,VEHICLE}})^2}$$

A post-hoc analysis of the data collected in the Phase 2 Dose Escalation Study 171-7151-201 (6) performed only for the subjects with 30-75 inflammatory lesions and 30-100 non-inflammatory lesions at baseline provided the following results for the least square means (i.e. the means obtained after having controlled for the fixed effects and the covariate of the ANCOVA) of the percent change from baseline in total lesions count and for the related sample size estimation.

	Number of subjects	Least Square Mean
TEST	24	-35.455503
VEHICLE	22	-14.144333

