3. Worst Case (WC): for each subject, missing values of a variable will be replaced with the worst value (failure in case of dichotomous variables or the higher value collected in the study for lesions counting) of that variable if the subject is assigned to the CB-03-01 arm and with the best value of that variable (success in case of dichotomous variables or the lower value collected in the study for lesions counting) if the subject is assigned to the Vehicle arm.
4. Last Observation Carried Forward (LOCF): for each subject, missing values of a variable are replaced by the last observed value of that variable.
5. Baseline Observation Carried Forward (BOCF): for each subject, missing values of a variable are replaced by the baseline observed value of that variable.

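### SAP 4.2.2 to 4.2.7 states the lesion-count hypotheses HT2 to HT7, including primary endpoints P2 and P3, in the wrong direction

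*SAP*

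**What the plan says.** SAP 4.2.2 to 4.2.4 define mu as the mean absolute change from baseline at Week 12 in each arm. Sections 4.2.5 to 4.2.7 define P as the mean percent change. For each of HT2 to HT7 the null is test minus vehicle at or below 0 and the alternative is above 0. For HT2 the alternative reads "H}_a: \mu_{\text{NILC,TEST}} - \mu_{\text{NILC,VEHICLE}} > 0", and for HT6 it reads "H_a: P_{NILC,TEST} - P_{NILC,VEHICLE} > 0".

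SAP 4.2 gives these statements a formal role: "The null hypotheses of the three hypothesis tests on the primary endpoints have all to be rejected in order to claim superiority". A failure to reject also stops all later tests.

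The sample size sections use the same quantities with negative values for improvement:

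- 4.3.2: "non-inflammatory lesions count of -22 for TEST treatment group and -1 for VEHICLE treatment group"
- 4.3.3: "inflammatory lesions count of -15 for TEST treatment group and -10 for VEHICLE treatment group"
- 4.3.4: "total lesions count of -35 for TEST treatment group and -13 for VEHICLE treatment group"

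Sections 4.3.5 to 4.3.7 do the same for percent change. In 6.4.1, the Worst Case rule gives vehicle subjects the best value, defined for lesions as "the lower value collected in the study for lesions counting".

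**The concern.** If change from baseline is negative when lesions clear, a better result on the test cream makes test minus vehicle negative. The printed alternative describes the opposite: the test cream clearing fewer lesions than vehicle. Taken literally, rejecting the printed null for P2 or P3 would show that the test cream is worse, yet SAP 4.2 would count that rejection towards a superiority claim. A true benefit would leave the null standing and stop the hierarchy.

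Nothing else in the plan formally states the direction for these endpoints. The protocol gives no inequalities. SAP 6.7.1.2 and 6.7.1.3 specify a comparison and a confidence interval but not which sign supports superiority. SAP 6.1 flags any p-value below 0.05 whatever its sign. A study report claiming superiority on P2 and P3 would have to depart from its own pre-specified hypotheses.

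**Working it through.** **1. Sign of the planned effects.** The planning means and the Phase 2 least square means both come from SAP 4.3.2 to 4.3.7. Each difference is test minus vehicle.

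| Test | Endpoint | Planning means | Difference | Least square mean difference |
|---|---|---|---|---|
| HT2 (P2) | NILC, absolute | -22 vs -1 | -21 | -22.398746 + 0.924803 = -21.47 |
| HT3 (P3) | ILC, absolute | -15 vs -10 | -5 | -14.473098 + 10.621723 = -3.85 |
| HT4 (S1) | TLC, absolute | -35 vs -13 | -22 | -35.7127562 + 13.0667959 = -22.65 |
| HT5 (S2) | TLC, percent | -35 vs -14 | -21 | -35.455503 + 14.144333 = -21.31 |
| HT6 (S3) | NILC, percent | -33 vs -5 | -28 | -33.718297 + 5.133111 = -28.59 |
| HT7 (S4) | ILC, percent | -37 vs -23 | -14 | -37.657976 + 23.450604 = -14.21 |

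All twelve differences are below 0, so each lies in the printed null region and none in the printed alternative.

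**2. Could change mean baseline minus Week 12?** That reading would make the printed sign right. It is excluded because 4.3.2 to 4.3.7 give the same quantities negative values, and the protocol's planning means are negative too.

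**3. Does the sign affect the sample size?** The SAP formula is N = 2 × SD² × (z for alpha/2 + z for beta)² / difference². SD is 17 for absolute change and 40 for percent change, alpha is 0.05 two-sided, and beta is 0.033 for HT2 and HT3 and 0.1 for HT4 to HT7.

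- (1.960 + 1.838)² is about 14.43, so 2 × 17² × 14.43 is about 8,339. HT2: 8,339/441 = 18.9, rounded up to 19. HT3: 8,339/25 = 333.6, rounded up to 334.
- (1.960 + 1.282)² is about 10.51. HT4: 12.6, rounded up to 13. HT5: 76.2, rounded up to 77. HT6: 42.9, rounded up to 43. HT7: 171.6, rounded up to 172.

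All six match the SAP. The formula squares the difference, so reversing the inequality changes nothing.

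**4. Rejection probability at 350 per group under the planning values** (normal approximation). SE = SD × sqrt(2/350), which is 1.285 for SD 17 and 3.024 for SD 40. In the printed direction the probability is Phi(difference/SE - 1.96). In the reversed direction it is Phi(-difference/SE - 1.96).

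| Test | Difference/SE | As printed | Reversed |
|---|---|---|---|
| HT2 | -16.34 | about 0 | >99.9% |
| HT3 | -3.89 | 2.4 × 10⁻⁹ | 97.3% |
| HT4 | -17.12 | about 0 | >99.9% |
| HT5 | -6.95 | about 0 | >99.9% |
| HT6 | -9.26 | about 0 | >99.9% |
| HT7 | -4.63 | 2.2 × 10⁻¹¹ | 99.6% |

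The reversed column equals the power of the specified two-sided tests to the precision shown.

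**5. Symbols.** Section 4.2.7 defines its quantity as "Mean percent change from baseline of ILC at Week 12 in TEST treatment group" but labels it with TLC subscripts, which duplicates the HT5 symbols.

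**The case against.** The best reply is that this is an erratum with no operative consequence. The section headings and the list in SAP 4.2 describe every test as superiority of the test cream over vehicle. The level is two-sided 0.05, the ANCOVAs report an adjusted difference with a 95% confidence interval, and 6.4.1 treats higher lesion counts as worse. An analyst following 6.7.1 and 6.7.2 would compute nothing differently. The six reversals are also one sign-convention slip carried through a template, not six separate errors. All of this stands, and it limits the weight of the point. It does not make the printed rule usable: the SAP ties the superiority claim to rejecting these particular nulls.

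Two further objections have merit. First, simply reversing the inequalities leaves one-sided hypotheses tested at a two-sided level, as HT1 already is, so a null of no difference plus a sign condition is the more complete rule. Second, the 97.3% for HT3 holds only for a difference of -5. With the unrounded -3.85, z = 3.85/1.285 = 3.00 and power is about 85%. With the -14 versus -11 printed in Protocol 17.2, z = 3/1.285 = 2.33 and power is about 65%. That is a separate inconsistency. The figures above show only that the sign slip does not alter power; they do not endorse the power for P3.

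**Conclusion.** The concern holds. Six of the seven printed hypotheses, including two of the three primary ones, point the wrong way against the SAP's own definitions and planning means. Applied literally, the decision rule for P2 and P3 gives the wrong conclusion. There is no effect on the models, estimates, two-sided p-values, confidence intervals, sample size or power. The conclusion rests only on reading change from baseline as the SAP itself uses it in 4.3, negative for improvement. It should be corrected, but it does not threaten the validity of the analysis.

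**What to change.** Preferred: for HT2 to HT7, state the null as a difference of 0 tested at two-sided 0.05. Add that superiority, and passage to the next test, require p < 0.05 with an adjusted test minus vehicle difference below 0. State the matching rule for HT1 (p < 0.05 with an odds ratio above 1).

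Minimum: reverse the inequalities, so that the null is a difference at or above 0 and the alternative is below 0.

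In the same edit, change the HT7 subscripts to ILC and correct the similar slips in the inputs of 4.3.2 (ILC symbols for NILC) and of 4.3.6 and 4.3.7 (TLC symbols for NILC and ILC).

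The cost is SAP wording only, to be made before database lock while the data are still blinded. Models, alpha, test order and sample size do not change.
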